1. INTRODUCTION, BACKGROUND & OBJECTIVE

Osteoarthritis or other degenerative changes or injury can cause damage to the structures in the knee, causing pain and discomfort, and lessening the quality of life. Knee replacement, or knee arthroplasty, is a common surgical procedure performed to relieve the pain and disability resulting from osteoarthritis. In general, the surgery consists of replacing the diseased or damaged joint surfaces of the knee with metal and plastic components shaped to allow continued motion of the knee.

Today, over 600,000 patients undergo total knee replacement each year in the United States, a number that is projected to increase greatly over the next 20 years (Kurtz). Total knee replacement has been performed since 1964 and has been shown to be an effective, long-lasting procedure with good survivorship of the implants for patients with osteoarthritis. Despite, the excellent survivorship, there are still a significant percentage of patients that remain dissatisfied with their results. Studies report 14-39% of patients report some level of dissatisfaction with their knees post-surgically (Noble et al., Bourne et al., Suda et al.).

The iTotal CR total knee replacement system and iPoly XE have been cleared by the FDA and CE marked for the treatment of osteoarthritis (OA). This study is designed to evaluate the clinical outcomes of subjects who have recently undergone surgery with the iTotal® Cruciate Retaining (CR) Total Knee Replacement System (KRS) who have also had iPoly XE Tibial Inserts implanted.

2. DEVICE DESCRIPTION

The iTotal® CR KRS is a tri-compartmental semi-constrained knee prosthesis composed of three components: a Femoral Component, a Tibial Component, and a Patellar Component. The product design incorporates a bone preserving approach for the treatment of severe pain and/or disability of a knee damaged by osteoarthritis or trauma. It is intended for use in those patients whose condition cannot be appropriately or effectively addressed using a device that treats only one or two compartments of the knee (i.e. a unicompartmental, bicompartamental, or patellofemoral prosthesis).

Using patient imaging, a patient-specific implant is designed that best meets the geometric and anatomic requirements of the specific patient. The treatment allows for the placement of a cemented metallic device designed from the patient's natural bone geometry. This process allows definition of the shape and size of the femoral and tibial components of the implant, as well as the disposable instrumentation (Fitz).

The iTotal® CR knee is constructed of cobalt chrome and conforms to the surface of the patient's femoral condyle, replacing the damaged cartilage with a smooth articulating surface. Specifically, the femoral component and tibial tray are manufactured from cobalt chromium molybdenum alloy. The tibial insert being utilized in this study will be a highly-crosslinked, Vitamin-E enriched UHMWPE (iPoly XE).

Several key features of the iTotal are listed below.

- Minimally traumatic procedure
- Precise fit to ensure range of motion without impingement or overhang

- Complete cortical rim coverage
- Anatomic component alignment
- Disposable, patient-specific instrumentation
- Simple, reproducible surgical technique
- Potential for less post-operative pain and shorter post-operative recovery time

3. STUDY DESIGN

The study is prospective and single-center. Subjects will be implanted with an iTotal® CR Knee Replacement System in conjunction with an iPoly XE insert. The study will include a minimum of 50 subjects and a maximum of 60 subjects at a single center. The study site will be located in Germany.

4. STUDY DURATION

The study subjects will be followed for 10 years post implant. The follow-up visit schedule will include on-site visits at 12 weeks, 6 months, 1 year, 2 years, 5 years and 10 years post implant to follow the surgeon's normal standard of practice. At 3, 4, 6, 7, 8, and 9 years post-op data may be collected; these data can be collected via phone call/email and do not require a subject to visit the site.

5. STUDY ENDPOINTS

5.1. Primary Endpoint

The study primary endpoint is pain and function at 1 Year after implantation, as measured by:

1. Knee Society Clinical Rating Score
 - 1.1. Objective Knee Score
 - 1.2. Function Score
 - 1.3. Satisfaction Score
 - 1.4. Expectation Score

5.2. Secondary Endpoints

The study secondary endpoints are:

1. The Knee Injury and Osteoarthritis Outcome Score (KOOS)
2. Revision rates post-implantation
3. Incidence of major procedure-related and device-related complications including infection rate
4. Post-operative limb alignment if long leg x-rays available
5. Radiographic loosening, radiolucencies
6. Length of procedure
7. Length of hospital stay in hours (admission to discharge)
8. Blood loss during surgery & blood transfusion rates

6. INCLUSION AND EXCLUSION CRITERIA

6.1. Inclusion Criteria

1. Clinical condition included in the approved Indications For Use for the iTotal® CR

2. Osteoarthritis, as confirmed by the investigator's assessment of disease status at screening visit that warrants a TKR procedure. Disease status is assessed by Clinical and Radiographic assessment.
3. Willingness to participate in the clinical study, to give informed consent, and to attend all follow-up visits
4. > 18 years of age

6.2. **Exclusion Criteria**

1. Simultaneous bilateral procedure required
2. BMI > 40
3. Active malignancy (defined as a history of any invasive malignancy – except non-melanoma skin cancer), unless patient has been treated with curative intent and there have been no clinical signs or symptoms of the malignancy for at least 5 years
4. Poorly controlled diabetes
5. Neuromuscular conditions which prevent patient from participating in study activities
6. Active local or systemic infection
7. Immunocompromised
8. Fibromyalgia or other general body pain related condition
9. Rheumatoid arthritis or other forms of inflammatory joint disease
10. Loss of bone or musculature, osteonecrosis, neuromuscular or vascular compromise in the area of the joint to be operated on, to an extent that the procedure is unjustified
11. Diagnosed with or receiving treatment for Osteoporosis
12. Other physical disability affecting the hips, spine, or contralateral knee
13. Severe instability due to advanced loss of osteochondral structure
14. Prior arthroplasty of the affected knee, including High Tibial Osteotomy (HTO)
15. Compromised PCL or collateral ligament
16. Severe fixed valgus or varus deformity of >15°
17. Extensor lag > 15°
18. Fixed flexion contracture ≥ 15°
19. Unwilling or unable to comply with study requirements
20. Participation in another clinical study which would confound results
21. Allergy to any of the implant materials

7. SITE SELECTION

The site will be selected by a Site Selection Committee based on a set of defined criteria. The Site Selection Committee will be led by Clinical Affairs. The site selection criteria includes, but is not limited to:

- Interest in participating in the study as demonstrated by responsiveness
- Demonstrated technical and surgical skills with iTotal® CR device - Investigator must have completed a cadaver training at minimum prior to enrolling their first patient
- Sufficient patient volume to expect timely subject enrollment
- Ability to adhere to the standards of Good Clinical Practice (GCP) and Good Documentation Practice (GDP)
- Clinical study experience and resources that demonstrate good compliance with study requirements and timely, complete documentation of subject follow-up

- Willingness to allow personnel from ConforMIS (or its designee) access to the hospital records, Investigator's study records, data, and patient files as they pertain to the study

8. ENROLLMENT

Potential subjects are identified by the Investigator or study staff based on patients' clinical and radiographic assessments during regular medical care. The Investigator or study staff provides study information and the approved Informed Consent Form to potential subjects and answers any questions. Once the patient signs the consent form, they are assigned a unique subject identification number through the EDC system that is comprised of a five digit number starting with a two digit site number assigned by ConforMIS at the Site Initiation followed by a three digit subject number, assigned chronologically for the entire study. For example, at site 01, the first subject enrolled will receive number 01-001, followed by 01-002, 01-003, etc.

The Investigator and/or study staff assesses the subject against the Inclusion and Exclusion criteria to determine eligibility. Eligibility includes clinical assessments, radiographic assessments and a review of the subject's medical history. The radiographic assessments should include:

1. Knee x-ray 3 views – AP, lateral, sunrise or Merchant
2. If site has the technology, three-foot standing x-ray (full length, full weight bearing film) – AP view

If the subject is not eligible to participate in the study, the subject is not enrolled and is considered a screen failure. All screen failures are tracked by the site manually in a tracking spreadsheet and electronically in a clinical database. Patient identification numbers for screen failures are not to be re-used.

The following Case Report Forms are required for all screen failures:

- SUBJECT INFORMATION
- INCUSION/EXCLUSION CRITERIA

If the subject is eligible to participate in the study, the subject is enrolled.

9. SCHEDULE OF EVALUATIONS BY VISIT

A table displaying the Schedule of Evaluations is in Appendix A. Enrolled subjects will complete each visit in the schedule of evaluations.

9.1. **Pre-operative Visit (Up to 4 months prior to Surgery)**

Many of the screening assessments required to ensure subject eligibility are also considered the pre-operative assessments. The results of the assessments are captured on the following Screening/Pre-operative Case Report Forms:

- SUBJECT INFORMATION
- INCLUSION/EXCLUSION CRITERIA
- MEDICAL HISTORY
- PAIN MEDICATIONS

- CONCOMITANT MEDICATIONS
- KNEE SOCIETY SCORE (Surgeon portion)

The subject completes the following questionnaires to assess pain and function as part of their pre-operative assessment:

- THE KNEE INJURY AND OSTEOARTHRITIS OUTCOME SCORE (KOOS)
- KNEE SOCIETY SCORE (Subject portion)

X-rays:

- 3 views – AP, lateral, sunrise or Merchant
- Three-foot standing x-ray (full length, full weight-bearing film): AP view

9.2. Surgery Visit (Day 0)

The Investigator surgically implants the iTotal® CR and iPoly XE inserts in compliance with the ConforMIS surgical training and iTotal® CR Instructions for Use.

The site completes the following Case Report Forms:

- SURGICAL SUMMARY
- DISCHARGE SUMMARY
- PAIN MEDICATIONS (update if changes have occurred)
- CONCOMITANT MEDICATIONS (update if changes have occurred)
- ADVERSE EVENTS / SERIOUS ADVERSE EVENTS (if any occur during surgery through discharge from hospital)

X-rays: None

9.3. 12-Week Follow-up Visit (± 2 weeks)

At the 12-week follow-up visit, the Investigator or study staff performs a post-operative knee assessment and identifies any adverse events that have occurred since the subject was discharged from the hospital.

The site completes the following Case Report Forms:

- FOLLOW-UP FORM
- KNEE SOCIETY SCORE (Surgeon portion)
- PAIN MEDICATIONS (update if changes have occurred)
- CONCOMITANT MEDICATIONS (update if changes have occurred)
- ADVERSE EVENTS (if any)
 - REVISION FORM (if necessary)

The subject completes the following questionnaires to assess post-operative pain and function:

- THE KNEE INJURY AND OSTEOARTHRITIS OUTCOME SCORE (KOOS)
- KNEE SOCIETY SCORE (Subject portion)

X-rays:

- 3 views – AP, lateral, sunrise or Merchant

- Three-foot standing x-ray (full length, full weight-bearing film): AP view

9.4. 6-Month follow-up visit (\pm 3 weeks)

At the 6-month follow-up visit, the Investigator or study staff performs knee assessments and identifies any adverse events that have occurred since the last visit.

The site completes the following Case Report Forms:

- FOLLOW-UP FORM
- KNEE SOCIETY SCORE (Surgeon portion)
- PAIN MEDICATIONS (update if changes have occurred)
- CONCOMITANT MEDICATIONS (update if changes have occurred)
- ADVERSE EVENTS (if any)
 - REVISION FORM (if necessary)

The subject completes the following questionnaires to assess post-operative pain and function:

- THE KNEE INJURY AND OSTEOARTHRITIS OUTCOME SCORE (KOOS)
- KNEE SOCIETY SCORE (Subject portion)

X-rays: None

9.5. Year 1, 2, and 5 Follow-up Visits (\pm 2 months)

At the 1-year, 2-year and 5-year follow-up visits, the Investigator or study staff performs a knee assessment and identifies any adverse events that have occurred since the subject's last visit.

The site completes the following Case Report Forms:

- FOLLOW-UP FORM
- KNEE SOCIETY SCORE (Surgeon portion)
- PAIN MEDICATIONS (update if changes have occurred)
- CONCOMITANT MEDICATIONS (update if changes have occurred)
- ADVERSE EVENTS (if any)
 - REVISION FORM (if necessary)

The subject completes the following questionnaires to assess post-operative pain and function:

- THE KNEE INJURY AND OSTEOARTHRITIS OUTCOME SCORE (KOOS)
- KNEE SOCIETY SCORE (Subject portion)

X-rays: Optional

9.6. Year 3, 4, 6, 7, 8, and 9 Follow-up Visits (\pm 3 months)

On the anniversary of the implant surgery for years 3, 4, 6, 7, 8, and 9, the Investigator or study staff assesses the subject for complications or adverse events, and specifically to determine if the iTotal® CR has been revised. It is not necessary for the subject to go to the clinic for a visit, as the site can obtain the data via direct communication with the subject (such as via telephone or email).

The site completes the following Case Report Form:

- FOLLOW-UP FORM
- ADVERSE EVENTS (if any)
 - REVISION FORM (if necessary)

X-rays: None

9.7. Year 10 Follow-up Visit (± 4 months)

On the 10-year anniversary of the implant surgery, the Investigator or study staff assesses the subject to determine if the iTotal® CR has been revised.

The site completes the following Case Report Form:

- FOLLOW-UP FORM
- PAIN MEDICATIONS
- CONCOMITANT MEDICATIONS
- ADVERSE EVENTS (if any)
 - REVISION FORM (if necessary)
- KNEE SOCIETY SCORE (Surgeon portion)
- SUBJECT DISPOSITION

The subject is asked to complete the following questionnaires to assess long term post-operative pain and function. Note that the subject should return to the clinic to complete these questionnaires. If a return to the clinic is not possible the patient will be provided the questionnaires either via mail, email, or through an internet site.

- THE KNEE INJURY AND OSTEOARTHRITIS OUTCOME SCORE (KOOS)
- KNEE SOCIETY SCORE (Subject portion)

X-rays: Optional

9.8. Early Termination Visit

In the event that the study subject ends their participation in the study prior to the 10-year visit, the investigator or designated study staff will complete the following CRFs:

- SUBJECT DISPOSITION
- PAIN MEDICATIONS
- CONCOMITANT MEDICATIONS
- ADVERSE EVENTS / SERIOUS ADVERSE EVENTS (if any)
 - REVISION FORM (if necessary)

The Investigator or designated study staff will make every attempt to complete the following CRFs (for both knees if necessary):

- THE KNEE INJURY AND OSTEOARTHRITIS OUTCOME SCORE (KOOS)
- KNEE SOCIETY SCORE (Subject and Surgeon portions)

10. SAFETY REPORTING

All Adverse Events (AEs) are recorded by the site from the day of surgery on the Adverse Event CRF and should be reported within 5 days of site becoming aware of the event. In addition, all Serious Adverse Events (SAEs) and Unanticipated Adverse Device Effects (UADEs) must be reported to ConforMIS or designee via telephone or email as soon as possible once discovered by the site. SAEs should be reported to ConforMIS within 3 working days, and UADEs should be reported to ConforMIS within 2 working days. The Investigator and investigative site will also be responsible for required reporting to the site's Institutional Review Board/Independent Ethics Committee (IRB/IEC).

For the purposes of this protocol, only those AEs categorized as Possible, Probable or Definite in relationship to the devices will be recorded. Those events that are Unlikely or Not Related to the device will not be collected. All Serious Adverse Events (SAEs) will be recorded regardless of the relationship to the device. Please see definitions below.

ConforMIS will be responsible for safety reporting as required by local regulations.

Adverse Event: Any untoward or unfavorable medical occurrence associated with the use of a medical product in a human patient, including any abnormal sign, symptom, or disease. Report only those AEs with Possible or above, relationship.

Definite:	Clear-cut temporal association and no other possible cause.
Probable:	Clear-cut temporal association and a potential alternative etiology is not apparent.
Possible:	Temporal association is less clear and other etiologies are also possible.
Unlikely:	Temporal association and the nature of the event is such that the study device is not likely to have had any association with the observed event (cause and effect relationship improbable but not impossible).
Not Related:	There is no temporal association and/or evidence exists that the event is definitely related to another etiology.

Serious Adverse Event: Any undesirable experience associated with the use of a medical product in a patient in which the patient outcome is: death, a life-threatening event, inpatient hospitalization or prolongation of existing hospitalization, a persistent or significant disability/incapacity, a congenital anomaly/birth defect or requires intervention to prevent permanent impairment or damage.

Unanticipated Adverse Device Effect (21 CFR 812.3): Any serious adverse effect on health or safety or any life-threatening problem or death caused by, or associated with, a device, if that effect, problem, or death was not previously identified in nature, severity, or degree of incidence in the investigational plan or application (including a supplementary plan or application), or any other unanticipated serious problem associated with a device that relates to the rights, safety, or welfare of patients.

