13. STATISTICAL METHODS

All statistical processing will be performed using SAS® Version 9.2 or later unless otherwise stated. Efficacy analyses performed using the intent-to-treat (ITT) population will be considered primary. Safety analyses will be performed on the safety population.

No imputations will be made for missing observations. Continuous variables will be summarized with sample size, mean, standard deviation, median, minimum, maximum, and 95% confidence intervals, as appropriate. Categorical variables will be summarized with frequency counts, percentages, and 95% confidence intervals, as appropriate.

Populations

The safety population will be comprised of all subjects for whom the procedure is initiated.

The ITT population will be comprised of all subjects for whom the procedure is completed.

Demographic and Baseline Evaluations

Demographic variables (age, gender, ethnicity, and race) will be recorded in the eCRF and summarized using descriptive statistics.

Efficacy Analysis

Primary Efficacy Analysis

There is one primary endpoint, change from baseline to 1-Year in KSS. Hypothesis testing of the primary endpoints will be conducted for the ITT population, and will be analyzed with paired t-test.

Secondary Efficacy Analyses

Secondary endpoints will be analyzed for the ITT population. Details of statistical testing for each endpoint will be further discussed in the Statistical Analysis Plan.

1. Change from baseline in KSS at years 2, 5 and 10 post-implantation
2. Change from baseline in KOOS at years 1, 2, 5 and 10 post-implantation
3. Post-operative limb alignment if long leg x-rays available
4. Length of hospital stay in hours (admission to discharge)
5. Blood loss during surgery
6. Transfusion rate

Supportive Efficacy Endpoints

1. Revision rates post-implantation
2. Radiographic loosening, radiolucencies
3. Length of procedure: Skin to Skin

Safety Analysis

All adverse events (AEs) occurring during the study will be recorded and classified. For the safety population, all reported AEs will be summarized by the number of subjects reporting AEs, severity, relationship to procedure, relationship to device, and seriousness. For summaries of AEs by relationship or severity, each subject will be counted only once using the event with the greatest relationship or highest severity.

In addition to overall AE summaries, AEs will be summarized for the following study periods:

- Day of procedure to 6 months post procedure

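### Section 10 says both that all adverse events are recorded and that non-serious ones are recorded only if device-related; if the restriction governs, Section 13's summary by relationship to procedure is incomplete

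*Combined protocol and SAP*

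**What the plan says.** Section 10 (Safety Reporting) contains two collection rules.

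- Its first sentence is unrestricted: "All Adverse Events (AEs) are recorded by the site from the day of surgery on the Adverse Event CRF".
- Its second paragraph, written for the purposes of this protocol, is restrictive: "only those AEs categorized as Possible, Probable or Definite in relationship to the devices will be recorded". It adds "Those events that are Unlikely or Not Related to the device will not be collected" and one exemption: "All Serious Adverse Events (SAEs) will be recorded regardless of the relationship to the device".
- The definition of an adverse event repeats the limit: "Report only those AEs with Possible or above, relationship".

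Section 13 (Statistical Methods, Safety Analysis) returns to the unrestricted version: "All adverse events (AEs) occurring during the study will be recorded and classified". For the safety population it then plans that "all reported AEs will be summarized by the number of subjects reporting AEs, severity, relationship to procedure, relationship to device, and seriousness". In the summaries by relationship or severity, a subject counts once, at the strongest relationship or highest severity. Further summaries cover the procedure day to six months, and yearly periods counted from the procedure day.

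The protocol history shows only version 1.0, so none of this is superseded text.

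**The concern.** A table can only show what was collected. Section 13 treats relationship to procedure and relationship to device as two separate attributes, but the restrictive rule in Section 10 selects non-serious events on the device attribute alone. A non-serious event caused by the operation and not by the implant could therefore be screened out before it reached the procedure table. A reader who had just been told that all AEs are recorded would take that table as complete.

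At stake is the descriptive safety account of the procedure, particularly in the peri-operative months. There is also a practical risk: site staff could apply either rule, and collection could differ from event to event over ten years of follow-up. Events that were never recorded may not be fully recoverable later.

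**Working it through.** The plan gives no figure to reproduce and no AE rates, so the check compares the texts.

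**Step 1: do the statements conflict?** Yes, in two places. Within Section 10, the opening sentence and the second paragraph give different rules. Between sections, Section 13's statement that all AEs are recorded and classified cannot hold alongside Section 10's statement that some will not be collected.

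**Step 2: which rule is likelier to operate?** The restriction is specific to this protocol, spells out what is excluded, carries its own exemption for SAEs, and is repeated in the AE definition. The unrestricted sentences are general. The restriction is the likelier rule, but this is an inference.

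**Step 3: what does the restriction keep?**

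| Event | Relationship to device | Collected? |
|---|---|---|
| Serious | Any | Yes |
| Non-serious | Possible, Probable or Definite | Yes |
| Non-serious, procedure-related | Unlikely or Not Related | No |
| Non-serious, not procedure-related | Unlikely or Not Related | No |

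The third row is the gap. The fourth row does not affect the count of procedure-related events.

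**Step 4: can an event fall in the third row?** Yes, on the protocol's own scale. Not Related is defined as "There is no temporal association and/or evidence exists that the event is definitely related to another etiology". An event firmly attributed to the operation has another etiology than the implant and can be rated that way. Section 10 asks only about the device and gives no rating for relationship to procedure, so nothing else in it brings such an event back.

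**Step 5: which way does the summary move?** The collected procedure-related events are a subset of all procedure-related events. Subjects with at least one collected event are therefore a subset of subjects with at least one event, and the reported count cannot exceed the true count. Because each subject is counted once at the strongest relationship, a subject whose only procedure-related event is missing drops out of the procedure-related count. A subject with another, weaker retained event appears at a lower level.

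**Step 6: what is untouched?** SAE summaries and listings, because SAEs are collected whatever their relationship; and the primary endpoint, which is change in Knee Society Score and does not use AE data.

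**The case against.** The strongest reply is that the tabulation sentence in Section 13 refers to reported AEs, and Section 10 uses the same verb when it limits what is to be reported. Read that way, the summary covers what was collected and is consistent with the filter. This stands as far as it goes: the contradiction lies in the sentence just before, which says that all AEs are recorded. The by-subject listing of AEs noted during the study is likewise compatible with the filter and is not evidence of conflict.

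Second, if the opening sentence of Section 10 governs, nothing is lost. This also stands, and it makes the consequence conditional.

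Third, the threshold is loose. Possible allows a less clear temporal association and other possible etiologies, so many peri-operative events of mixed cause would be kept. This limits the gap but does not close it.

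Fourth, device-only collection is a legitimate choice for a device that Section 1 describes as FDA-cleared and CE marked. Agreed; the choice is not the fault. What needs correcting is the promise of all AEs, and an unlabelled analysis by an attribute that played no part in selecting the non-serious events.

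A reader might go further and infer that the events most firmly tied to the procedure are the ones most surely removed. That needs the device scale to be used for the procedure too, which the documents do not say. A reader might also infer that the infection rate in Section 5.2 will be undercounted. That would require the endpoint, worded as major complications, to include non-serious infections; those infections to be rated below Possible for the device; and no other form to capture them. The documents establish none of these.

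**Conclusion.** The contradiction is certain: it is in the current text, both within Section 10 and between Sections 10 and 13. The effect on the safety summaries is conditional on the device-only filter governing, which is the likelier reading. On that reading, the summaries by relationship to procedure, overall and for the procedure day to six months, cover only SAEs plus device-related AEs, and any error is an understatement. The yearly summaries, which start from the same day, would inherit the gap.

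The size cannot be derived. It depends on how many non-serious events are related to the procedure and rated Unlikely or Not Related to the device, and the documents give nothing from which to estimate that. It would be wrong to read this as showing that events will certainly be lost, or that many will be. The point should be fixed because a planned safety table may mean something other than what its text says. It does not threaten the primary result or the SAE reporting.

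**What to change.** Reconcile Sections 10 and 13 in one of two ways. Both remove the contradiction, and the choice is the sponsor's.

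(a) **Widen collection.** Record non-serious AEs rated Possible or above in relation to the device or the procedure, plus all SAEs. State in Section 10 how relationship to procedure is rated, and align the opening sentence and AE definition of Section 10 and the recording sentence of Section 13 with this rule. Cost: wording, some extra AE entries (number not derivable from the documents), and possibly one field on the AE form if it is not already there. No extra visits or subjects.

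(b) **Keep the device-only filter.** Correct the sentences in Sections 10 and 13 that promise all AEs, and label the procedure-relationship summaries, including those by period, as covering only SAEs and device-related AEs. Cost: wording only. The summary would then be accurately described, but non-serious procedure-related events outside the filter would remain unknown.
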